**1= No distraction or no impact****10= Most distraction or most impact**

|   | 1                     | 2                     | 3                     | 4                     | 5                     | 6                     | 7                     | 8                     | 9                     | 10                    |
|---|-----------------------|-----------------------|-----------------------|-----------------------|-----------------------|-----------------------|-----------------------|-----------------------|-----------------------|-----------------------|
| To what degree, if any, did the exercise distract you from performing or assisting in the surgical procedure? |  |
| To what degree, if any, would you say that the exercises impacted the flow of the surgery?                    |  |

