### ● Sample size

- N= 26
  - 9 attending physicians and 8 residents at GWU
  - 9 attending physicians at Children's National Medical Center

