### ● Recruitment Methods

- An E-mail will be sent out to attending physicians and residents affiliated at GWU and Children's National inviting them to participate in the study.

- **Research Locations**

- George Washington University Hospital
- Children's National Medical Center

[figure not shown]
- **Methods**

- **Intervention**

- **Otolaryngology stretching micro-breaks (OSMB)**= standardized microbreak stretch that is designed to perform intraoperatively within the sterile field at medically convenient 20-40 min intervals throughout each procedure.

- **Assessment tools (see the table of content to view survey)**

[figure not shown]
- Preliminary questionnaire- given at the beginning of the study
    - Assess demographic information, ergonomic questions, and musculoskeletal symptom questions
  - Pre-surgery questionnaire (baseline)- given prior to each surgery to establish a baseline
    - Body part discomfort (validated survey with 0-5 score on the neck, shoulder R/L, hand R/L, lower/upper back, knee R/L, foot R/L)

- Post-surgery questionnaire for CONTROL day- given after each surgery
  - Surg-TLX and GOAL questionnaire- assess the degree of difficulty of the surgery
  - Body part discomfort sore
- Post-surgery questionnaire for INTERVENTION day- - given after each surgery
  - Surg-TLX and GOAL questionnaire- assess the degree of difficulty of the surgery
  - Body part discomfort sore
  - Questions on OSMB
- Exit questionnaire after the study is completed
  - 2 questions asking whether the participant would incorporate OSMB in their routine OR cases, and would recommend OSMB to colleagues.

- **Study design**

- Crossover study design
- Control: 3 Non-OSMB surgical days
- Intervention: 3 OSMB surgical days
- In order to reduce confounding variables, study will focus on open neck cases. (e.g. thyroidectomy, parathyroidectomy, neck dissection, etc)
- We will adjust for surgical duration, and use Surg-TLX, and GOAL questionnaires to show no statistically significant difference between control and intervention surgical cases.
- Outcome measures
  - Primary outcome= difference between self-reported body part discomfort score from before/after surgery
    - Control the surgical environment and difficulty using Surg-TLX and GOAL questionnaires. The score should be statistically insignificant among various surgeries.
  - Secondary outcome= impact of OSMB on physical performance, discomfort/pain, fatigue, and mental focus

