#### Demographic information

Today's date

---

What is your gender?

- Male
- Female
- Transgender
- Other
- Prefer not to answer

Other (please specify)

---

What is your age?

---

What is your height in inches?

---

What is your weight in pounds?

---

BMI

---

What is your dominant hand?

- Left
- Right
- Both

What is your surgical title?

- Resident
- Fellow
- Attending

What is your postgraduate year (PGY) equivalent level?

- PGY1
- PGY2
- PGY3
- PGY4
- PGY5

How many years of surgical training and/or practice have you completed?

- 0-1 year
- 2-5 years
- 6-10 years
- 11-20 years
- Over 20 years

How many days a week do you perform surgery?

---

How many cases do you perform on a surgery day?

---

Confidential

Page 2 of 4

What is the average duration of each case in hours?

Do you have an exercise routine?

Yes  
 No

How many days a week do you exercise?

What form of exercise(s) do you perform? (select all that applies)

Stretching  
 Yoga  
 Pilates  
 Strength training  
 Cardio training (running, walking, swimming, cycling, etc.)  
 Other

Other (please specify)

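### No form carries a case number, case order or role, so on multi-case days pre- and post-surgery scores cannot be paired with certainty, and two reports on one operation cannot be linked

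*Protocol*

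**What the plan says.** **Design and outcome (Protocol, Study design and Assessment tools).** Each participant has two sets of days: "Control: 3 Non-OSMB surgical days" and "Intervention: 3 OSMB surgical days". Forms are completed per operation. The pre-surgery form is "given prior to each surgery to establish a baseline", and the control version of the later form is listed as "Post-surgery questionnaire for CONTROL day- given after each surgery"; the intervention version has the same timing. The primary outcome is the change in body part discomfort from before to after surgery. The protocol also plans to adjust for surgical duration.

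**Cases per day (Preliminary questionnaire, Demographic information).** Participants are asked "How many cases do you perform on a surgery day".

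**Who takes part (Sample size).** The list is "9 attending physicians and 8 residents at GWU" and "9 attending physicians at Children's National Medical Center". The distraction item on the intervention form asks to what degree "did the exercise distract you from performing or assisting in the surgical procedure".

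**What the forms record.**

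| Form | Identifiers | Case items |
|---|---|---|
| Pre-surgery | Record ID, date | none |
| Post-surgery control | Record ID, date | case type, duration, difficulty and workload, position, equipment |
| Post-surgery intervention | Record ID, date | as control, plus micro-break items |

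Record ID is not defined. It also appears on the preliminary and exit questionnaires. No form has a case number, the order of the case that day, or whether the respondent was operating or assisting.

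**Analysis (Statistics).** Linear mixed models are planned, with significance at 0.05 and a Bonferroni adjustment for 11 body parts. No grouping factors are named.

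**The concern.** A change score needs the right pre-form next to the right post-form. If a surgeon records two open neck cases on one day, Record ID and date (taking Record ID as a person key) return two pre-forms and two post-forms. Nothing on the pre-form says which case it belongs to, because case type and duration are asked only afterwards.

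The second gap concerns shared operations. If an attending and a resident both report on one case, their scores share its length, its difficulty and its break pattern. An analysis with only a participant effect would count those reports as separate evidence, and without a linking field no model can do otherwise.

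Both are faults of data collection. A statistical analysis plan can choose the random effects, but it cannot restore a link that the forms did not capture.

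**Working it through.** **1. The plan's own figures.** The head count reproduces: 9 + 8 + 9 = 26. With 3 + 3 = 6 days each, one report per participant-day gives 26 × 6 = 156 reports. The Bonferroni level is 0.05/11 = 0.0045.

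**2. Pairing.** With k complete cases on one day there are k! ways to match pre- to post-forms: 1, 2, 6 and 24 for k = 1, 2, 3 and 4.

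What a wrong match does can be seen in a made-up three-case day with pre-scores 2, 3, 4 and post-scores 5, 1, 1:

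- Mean change is (5 + 1 + 1 − 2 − 3 − 4)/3 = −0.67 under all six matchings.
- The variance of the three changes is 2.33, 6.33 or 10.33, depending on the matching.

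So with complete forms the day's mean is safe. Condition is set by day, so an unadjusted comparison of day means is safe too. Three things are not:

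- the case-level changes and their variance;
- the adjustment for duration, which is recorded per case on the post-form and would be attached to the wrong change;
- any multi-case day with a missing form, where even the mean of the usable pairs depends on which forms are matched.

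**3. Shared operations.** The protocol gives neither the overlap nor the within-case correlation ρ, so both are assumed. Take two-sided tests, one report per participant-day, and all 8 × 6 = 48 resident reports each sharing an operation with one attending report on the same condition. Then 96 of 156 reports are in pairs (the same share as 16 of 26 participants), and

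variance factor = [60 + 96(1 + ρ)]/156 = 1 + ρ × 16/26

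actual error = 2[1 − Φ(z/√factor)], with z the two-sided critical value at the nominal level.

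| ρ | Variance factor | Effective reports | Error at nominal 0.0045 | Error at nominal 0.05 |
|---|---|---|---|---|
| 0.1 | 1.06 | 147 | 0.006 | 0.057 |
| 0.3 | 1.18 | 132 | 0.009 | 0.072 |
| 0.5 | 1.31 | 119 | 0.013 | 0.087 |

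**4. Sensitivity to overlap.** The same formula, with ρ from 0.1 to 0.5:

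- Half of those cases shared, same condition: factor 1.03 to 1.15, error 0.005 to 0.008 at nominal 0.0045.
- No sharing, or sharing split evenly between same and opposite conditions: factor 1, no inflation.
- All shared, always on opposite conditions: factor 1 − ρ × 16/26 = 0.94 to 0.69, error 0.043 to 0.019 at nominal 0.05. The test is then conservative.

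**The case against.** Several objections have force.

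- **The protocol does not say that reports will be treated as independent.** A reader might infer it from the bare mention of linear mixed models, but grouping factors are commonly left to the statistical analysis plan, which is not shown. What stands is narrower: an operation effect cannot be fitted reliably without a field that identifies the operation.
- **Joint reporting by attending and resident is not stated.** It is an inference from the enrolment list and the wording about assisting. An assistant may report on a case whose operating surgeon is not a participant. It is possible, and nothing excludes it.
- **Several study cases per day are not stated either.** The question about cases per day concerns usual practice, study cases are limited to open neck operations, and the post-forms ask about the day's case in the singular. Completion at each surgery still leaves several per day open.
- **Record ID might be a case key, or the survey system might hold timestamps.** The document says neither. Use of the same field on the once-only preliminary and exit forms suggests a person key. If it were a case key, the surgery forms would show no link to the participant, which a crossover analysis needs.
- **The planned adjustment for duration may absorb part of the within-case correlation.** This is fair, and another reason to treat the figures above as high.

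A reader might also infer that one shared operation brings both inflated error and contamination of control cases. It cannot: inflation needs the two members on the same condition, contamination needs them on opposite ones. The documents give no basis for a contamination rate, so no dilution figure is offered.

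**Conclusion.** The point holds as a gap in the forms. On any day with two or more study cases, the forms as printed do not allow certain pairing for the primary outcome. The harm falls on case-level changes, the duration adjustment and days with a missing form, not on complete-day means. Its size cannot be given, because the number of study cases per day is not stated.

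The clustering part is conditional. For ρ of 0.1 to 0.5, a variance factor of 1.06 to 1.31 and a per-test error of about 0.006 to 0.013 against 0.0045 are the upper end. They need every resident case to be shared with an attending on the same condition and the sharing to be ignored in the analysis. The true effect may be smaller, nil or in the conservative direction. The case for acting rests mainly on the pairing: the primary outcome depends on it, the remedy is cheap, and a link not collected at the time may not be recoverable.

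**What to change.** - Define Record ID as the participant key.
- Add three fields to the pre-surgery form and both post-surgery forms: a coded operation number, the same for every participant in that operation; the order of the case that day; and role (operating or assisting).
- Pair pre- and post-forms on participant and operation number.
- Where operations are shared, include a random effect for operation as well as for participant.

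The cost is three short fields per form and possibly slightly wider intervals. The fields must be in place before data collection. Fixing the condition for whole operating teams is not proposed: it is a larger design trade-off, and it would rest on overlap that the protocol does not establish.

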  - Tertiary outcome= distraction and workflow interruption of OSMB

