### Post-surgery intervention

Record ID

Today's date

What case have you performed today?

[figure not shown]
- Thyroid
- Parathyroid
- Open neck
- Facial trauma
- Neck trauma
- Other

Other (please specify)

How long was the case? (in hours)

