#### GOAL and Surg-TLX subscales

[figure not shown]
Degree of difficulty- This procedure was:

[figure not shown]
Task Complexity: How complex was the procedure?

[figure not shown]
Distraction: How distracting was the operating environment?

Mental Demand: How mentally demanding was the procedure?

Physical demand: How physically demanding was the procedure?

Confidential

Page 2 of 3

**Body part discomfort scores:****1 Not uncomfortable****2 Barely uncomfortable****3 Quite uncomfortable****4 Very uncomfortable****5 Extremely uncomfortable**

|                 | 1                     | 2                     | 3                     | 4                     | 5                     |
|-----------------|-----------------------|-----------------------|-----------------------|-----------------------|-----------------------|
| Neck            |  |
| Shoulder, right |  |
| Shoulder, left  |  |
| Hand, right     |  |
| Hand, left      |  |
| Lower back      |  |
| Upper back      |  |
| Knee, right     |  |
| Knee, left      |  |
| Foot, right     |  |
| Foot, left      |  |

What was your primary position during the surgery?

Standing  
 Seated  
 Standing and Seated

What surgical equipments have you used during the case? (select all that applies)

Headlight  
 Robot  
 Laparoscopic equipment  
 Loupes  
 Microscope  
 Other

Other (please specify)

How often have you performed micro-break stretches?

Every 20 minutes  
 Every 30 minutes  
 Every 45 minutes  
 Every hour  
 Every 1.5 hours  
 Every 2 hours  
 Random time

How many micro-break stretches have you performed during the surgery?

Confidential

Page 3 of 3

| What is the impact of microbreak stretches have on... | Diminished            | Did not change        | Improved              |
|---|-----------------------|-----------------------|-----------------------|
| Physical performance                                  |  |  |  |
| Discomfort and pain                                   |  |  |  |
| Fatigue   |  |  |  |

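### The only rating of surgical flow gives no direction of impact, so high scores cannot be read unambiguously as the workflow interruption named as a tertiary outcome (minor)

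*Protocol*

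**What the plan says.** Under Outcome measures in the Study design section, the Protocol states "Tertiary outcome= distraction and workflow interruption of OSMB". Both parts are costs of the intervention.

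The last page of the Post-surgery Intervention questionnaire has a two-row grid that serves this outcome. The first row asks "To what degree, if any, did the exercise distract you from performing or assisting in the surgical procedure". The second asks "To what degree, if any, would you say that the exercises impacted the flow of the surgery". Both rows share one pair of anchors, "1= No distraction or no impact" and "10= Most distraction or most impact".

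Directly above is a separate grid headed "What is the impact of microbreak stretches have on". It lists physical performance, discomfort and pain, fatigue, and mental focus, with the choices diminished, did not change or improved. Flow is not in that list.

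**The concern.** The outcome is directional and the item is not. The tertiary outcome concerns interruption, but the flow item asks only for the size of an impact. Taken literally, a surgeon whose flow was badly broken and one whose flow became much smoother would both mark a high number.

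The form itself treats *impact* as something that can go either way. The grid just above uses the word and offers both a worse and a better answer. A surgeon who has just marked an improvement there may carry that sense into the flow question.

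At stake is what the trial can say about the intraoperative cost of the breaks. The distraction and flow items are its direct ratings of that cost, and any statement about interruption would rest mainly on the flow item. Direction is lost when the answer is given, so a statistical analysis plan could not restore it.

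**Working it through.** The Protocol gives no figure to reproduce. The check sets the outcome against every item that could measure it.

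**Does any item give the direction of the effect on flow?**

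| Item | Form | What it rates | Direction for flow? |
|---|---|---|---|
| Flow item | Post-surgery Intervention | Size of impact on flow, 1 to 10 | No |
| Distraction item | Post-surgery Intervention | Distraction by the exercise, 1 to 10 | Clearly adverse, but not about flow |
| Impact grid | Post-surgery Intervention | Performance, discomfort, fatigue, focus | Directional, but flow is not listed |
| "Distraction: How distracting was the operating environment" | Both post-surgery forms | The operating environment | Not about flow or the exercises |
| Case length in hours | Both post-surgery forms | Duration, which Study design uses for adjustment | Not a rating of flow |
| Exit questionnaire | Exit | Willingness to adopt and to recommend | No flow item |

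Only the flow item rates flow, and nothing else supplies its direction.

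**What can a score mean?** Let I be the score a surgeon would give on a pure interruption scale from 1 to 10, and Y the score actually marked.

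- If the surgeon takes *impact* as adverse, Y = I.
- If the surgeon was not interrupted but counts smoother flow as impact, I = 1 and Y is above 1.
- In both cases Y ≥ I, so the mean of Y is at least the mean of I.

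It follows that Y = 1 excludes interruption, a low mean bounds interruption from above, and a high mean may be interruption, improvement or a mixture. The inequality assumes that an interrupted surgeon does not offset the interruption against a benefit and mark a smaller net impact.

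**How large could the overstatement be?** If a share p of ratings comes from surgeons with improved flow who mark s where the interruption score would be 1, the mean is inflated by p × (s − 1). The Protocol gives neither p nor s, so the values below are assumptions.

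- p = 0: inflation 0.
- p = 0.2, s = 2: 0.2 × 1 = 0.2 points.
- p = 0.2, s = 7: 0.2 × 6 = 1.2 points. If the other 80% mark 2, the mean is 0.8 × 2 + 0.2 × 7 = 3.0, against 0.8 × 2 + 0.2 × 1 = 1.8 on an interruption scale.
- p = 0.2, s = 10: 0.2 × 9 = 1.8 points.

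With the planned 26 participants contributing equally, a share of 0.2 is 0.2 × 26 = 5.2, or about five surgeons. These figures show the mechanism and do not estimate how often it would occur.

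**The case against.** The best defence is context. The flow item is the second row of a grid whose first row is plainly adverse, and the shared anchors pair impact with distraction. Benefits have their own grid just above, so a surgeon who felt better has already had a place to say so. The intervention is itself a pause for stretching, and the Protocol gives no reason to expect a pause to be rated as strongly improving flow. Many respondents will probably take the item as adverse. This stands, and it limits the severity. It does not remove the defect, because the form never states the adverse meaning and the grid above uses *impact* in both senses.

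A reader might infer something stronger: that interruption cannot be read from the item at all, so the trial cannot say whether OSMB interrupts surgery. The Protocol does not support that. A score of 1 means no impact and hence no interruption, and a low result would be evidence of little interruption.

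A reader might also think that a surgeon whose flow improved hides an effect by marking 1. For the declared outcome, 1 is the right answer in that case. Improved flow is not an outcome anywhere in the Protocol, so nothing it set out to measure is lost.

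**Conclusion.** The item does not match its declared outcome, and the mismatch runs one way: it can overstate interruption. A low result remains usable and a high one would be ambiguous. This rests on the literal wording of the question and anchors, and on interrupted surgeons not reporting a net effect. The size cannot be fixed from the Protocol. It is zero if every surgeon takes the item as adverse, and it grows with the share who do not.

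The scope is narrow: half of a tertiary outcome. The distraction half has a clear item of its own. The body part discomfort score, the secondary impact ratings and the mixed model are unaffected. Severity is minor.

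**What to change.** Reword the flow item to: *To what degree, if any, did the exercises interrupt or slow the flow of the surgery?* Change the shared anchors to 1 = no distraction or no interruption, and 10 = most distraction or most interruption. The item then asks for what the tertiary outcome names.

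The cost is one question and one anchor pair on one form, with no effect on the design, sample size or primary analysis. The downside is that any answers already collected under the present wording would not be directly comparable. They should be reported separately and described as undirected impact.

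A flow row in the grid of diminished, did not change and improved would also capture benefit. That is optional, since the Protocol does not declare improved flow as an outcome.

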## Exit Questionnaire

*Confidential*

*Ergonomic survey*  
Page 1 of 1

### Exit questionnaire

---

Record ID

---

---

Today's date

---

Would you like to incorporate the microbreak into  
your OR routine?

Yes  
 No

---

Would you recommend microbreak to your colleagues?

Yes  
 No
